Nurse practitioners or physician assistants in the Ortho-Joint located at [name] will ask their patients during their preoperative visits if they would like to be contacted about a pain study. These forms, known as “okay to contact” forms, should be picked up at the ortho-joint clinic weekly. When the status of a participant is determined, the okay to contact forms should be placed in the appropriately labeled binder (one binder per study calendar year) and locked. The coordinator will review the patient’s EPIC health record to collect the necessary information to create a REDCap record for the participant.

Screening & Eligibility Forms

Screening information will be maintained electronically in the REDCap enrollment project, in the “Initial Eligibility Survey” instrument or “COORD: Consent Call” instrument. Screening information will be compiled regularly into a report detailing the patient name, the date the screening occurred, the method of screening, the study team member performing the screen (if applicable), the screening result (eligible, ineligible, declined to participate and reason), whether the patient was enrolled, and any comments.

Consent Forms

Electronic Consent forms will be stored in PDF format in the File Repository of the REDCap MAP-Pain Enrollment Project. Hard copy consent forms should be scanned and uploaded to the REDCap File Repository as backup storage. Physical Copies of consent forms will be stored in a study binder in a secure cabinet.

For every consent form that is signed, regardless of method of signing, a copy of the signed form must be sent to the participant. For those signing online, a *secure* email (sent by writing “Secure:” in the subject line) with the signed consent attached must be sent. For those signing in paper form, a hard copy of the signed form must be sent via mail.

MAP-Pain Standard Operating Procedures

For Intervention participants, a copy of the consent form will also be sent to Medical Records for storage in the patient's chart; this will have the patient's MRN on each page. The electronic consent document from REDCap will be printed out and will include an electronic version of the study bar code, or a sticker with the study bar code. It is then sent to HIMS, room HC032, MC5200, with coordinator's contact information included. If asked, MAP-Pain has been IRB approved to use the eConsent method; participant names typed into the eConsent form are in lieu of signatures.

Patient Adherence

Non-adherence is considered greater than recommended opioid use that is still within the range of the patient's prescription.

Patient Retention

Patient retention is at its highest rate when participants feel like they are aware of what is occurring in the study, when they have their needs met, and when they are greeted with optimistic and attentive staff.

To keep participants engaged:

- Research staff must ensure that participants know exactly what the study goals are and how the study staff are working to meet these goals.
- Participants should be completely aware of what is required for effective, active participation. The level of time commitment must be made clear at the beginning in order to avoid future dissatisfaction.
- Participants should know that we greatly appreciate their efforts, especially since they are volunteering their time. It must be made clear how important their contribution is to this science.
- Participants must be told that they can withdraw from the study at any time even though we would be sad to let them go. They must be made aware of the effort it takes on all fronts in designing this study and collecting data, so they should try their best to remain in the study.
- Research staff must ensure that all other staff know what to communicate to participants, especially in times of dissatisfaction.

To retain participants who are dissatisfied with the study:

- If the issue comes from participants feeling overwhelmed by assessments, research staff must make an effort to reduce assessments. (See *Survey Frequency Reduction* above)

MAP-Pain Standard Operating Procedures

Trial Safety

Potential Risks & Response to Risks

Risk of Telephone Contact

The primary risk of telephone and online contact involves breach of confidentiality. All research personnel are trained in confidentiality procedures and adequate protections will be in place to minimize this risk. All research personnel must be HIPAA trained. Personnel enrolling participants must complete CITI training.

Risks of Intervention

In addition to risks of confidentiality, there are few other risks involved in enrollment into the intervention. Those who are randomized into MI+GOW may be exposed to greater risk. These risks, however, are only relevant if a participant follows the recommendations. Because [name] is not a part of a participant's regular care team, the participant has the freedom to choose which recommendations to follow, with no obligation to follow any at all. [name]'s role is to recommend courses of action that meet the participant's needs, to the extent that it does not do additional medical harm.

Despite these rules, the following are risks that may be associated with participating in MI.

The physical and psychological risks to subjects are the effects opioid withdrawal including tachycardia, diaphoresis, restlessness, rhinorrhea, bone or joint aches, gastrointestinal upset, tremor, irritability, anxiety, and piloerection. Also, patients may experience increased pain if opioids are tapered prematurely. The seriousness of these side effects is moderate, as withdrawal symptoms and pain will be monitored during the intervention. Protocols are in place to hold the tapering schedule with the development of moderate opioid withdrawal and to increase the opioid dose with the development of severe pain. This type of opioid withdrawal is not fatal (as opposed to iatrogenic opioid withdrawal precipitated by opioid antagonists that could lead to mortality). Patients will be encouraged to contact the nurse practitioner ([name]) at any time regarding the development of any adverse effects. Patients will be able to reach the PI ([name]) or an alternate qualified member of the research team 24 hours a day. Also, participants reporting dramatically increased pain potentially related to other medical causes-e.g. infection, dislocation, thromboembolic disease, new neurologic deficits, will be referred to their nearest emergency department, and their PCP or surgeon will be contacted at the discretion of [name] or [name].

The alternative treatment is enhanced usual care, and a subset of these participants is at risk for delayed opioid cessation and potential opioid misuse and abuse. Although participants will be instructed to call 911, or to seek immediate medical attention for medical emergencies, we will encourage participants to call regarding any questions or unusual symptoms they are experiencing. Also, participants will be instructed to contact their primary care provider or surgeon for medical questions unrelated to the study.

MAP-Pain Standard Operating Procedures

Trial Stopping Rules

Given that the research does not involve a high-risk intervention or a population based on previous studies, absolute stopping rules will not be identified in the statistical plan. Any individual participant may choose to end participation for any reason, and this will be noted. The PI may choose to end an individual participant's participation if the participant is non-compliant with study procedures such that the study integrity is harmed or the participant is put at risk by continued participation.

Reporting Study Events to the IRB

Adverse Event Reporting

An adverse event is defined as any undesirable symptom or event experienced by the participant while he/she is in the study. An adverse event can be expected, unexpected, related, or unrelated to the study. If the event does not require great intervention and is addressed by the participant's normal care team, it can be recorded as a study adverse event and does not have to be reported to the IRB.

Serious Adverse Event Reporting

Serious adverse events (SAEs) are defined as:

- Life-threatening
- Fatal/Death
- Hospitalization/prolongation of hospitalization
- Congenital anomaly
- Persistent or significant disability/incapacity
- Required intervention to prevent permanent impairment/damage

SAEs must be tracked using the NIDA SAE form. The PI/Coordinator will report all SAEs in the annual report to NIDA, including any IRB recommendations on SAEs related to the study. All adverse events will be recorded and reported in aggregate on an annual basis to NIDA, as well as the IRB, and quarterly to the DSMB.

Any unexpected events will be reviewed by the Research Manager, in consultation with the PI, for determination as to whether it meets the definition of an Unanticipated Problem. If determined to be an Unanticipated Problem, or any of the following below, the issue must be reported to the IRB within 10 working days.

- a. New Information that indicates a change to the risks or potential benefits of the research in terms of severity or frequency or impacts the subject's willingness to participate
- b. Noncompliance: An action or activity in human subject research at variance with the approved IRB protocol, other requirements and determinations of the IRB, the HRPP Policy Manual and other applicable policies of Stanford University, SHC, LPCH, VAPAHCs

MAP-Pain Standard Operating Procedures

(e.g., VHA Handbook 1200.5), Palo Alto Veterans Institute for Research (PAVIR) or relevant state or federal laws. When the event is:

- Possibly serious: Noncompliance that affects the rights or welfare of human subject research participants.
- Possibly continuing: A pattern of noncompliance that continues to occur after a report of noncompliance and a corrective action plan has been reviewed and approved by the IRB, after an investigator has been warned to correct errors or noncompliance, or a circumstance in which an investigator fails to cooperate with investigating or correcting non-compliance.
- c. Complaint unresolved by the research team
- d. Incarceration when in the opinion of the PD it is in the best interest of the participant to remain on the study.
- e. Other events or information: Examples include a deviation intended to eliminate an immediate hazard to a participant, suicide or suicide attempt of a participant, other Audit or Monitoring Visit reports and Corrective Action Preventative Action (CAPA) plans. Report only after consulting with the IRB Panel Manager.

Unexpected deaths or life-threatening experiences related to the research (at Stanford, or when STANFORD is the coordinating institution in a multi-site study) must be reported to the IRB within 5 working days from PD learning of event.

Unanticipated Problems Involving Risks to Participants or Others (UPs): Events (internal or external, deaths, life-threatening experiences, injuries, or other) occurring during the research study, which in the opinion of the Monitoring Entity or the PD meet all of the following criteria:

a) Unexpected

in terms of nature, severity, or frequency, given (a) the research procedures described in the protocol-related documents, and (b) the characteristics of the subject population being studied;

AND

b) Related to participation in the research or there is a reasonable possibility or likelihood that the incident, experience, or outcome may have been caused by the procedures involved in the research;

AND

c) Harmful: the research places subjects or others at a greater risk of harm (including physical, psychological, economic, or social harm) than was previously known or recognized

All records of trial safety must be documented and stored in the “Trial Safety” folder of the STOP server.

MAP-Pain Standard Operating Procedures

Trial Monitoring

Adverse Events, Serious Adverse Events, Unanticipated Problems, and Protocol Deviations will be monitored on a continual basis and reported per information in the Study Events section.

Patient Adherence will be monitored as described in the relevant section, and in Compliance Monitoring section above.

The PI will hold regular staff meetings at least twice monthly to assess study team member understanding of responsibilities as per the Education section.

The first 10 participants will have case report forms and consent forms reviewed for accuracy and completion immediately after enrollment and entry into the follow-up period. After the first ten participants, case report forms and consent forms will be evaluated for completeness every 50 participants, or every 3 months. The results of these evaluations will be discussed at the quarterly DSMB meeting.

Participant Monitoring

The research team must check all active participants in REDCap at least once a week to identify any missing assessments, and to call participants with reminders to complete the assessments.

Data Safety and Monitoring Plan

Ultimately, the PI will be responsible for monitoring the safety and efficacy of this trial, executing the Data and Safety Monitoring (DSM) plan, and complying with the reporting requirements. In addition, [name] will conduct periodic internal reviews to monitor the trial with a rotating panel of 2 additional physicians, and 2 Stanford Systems Neuroscience and Pain Lab members. The Stanford Systems Neuroscience and Pain Lab members will have with no conflicts of interest with, or financial stakes in the research outcomes that would make them ineligible to participate in the internal review.

Frequency of DSM

The internal committee will analyze the DSM monitoring report every 3 months in the course of the trial. At minimum, [name] will meet with one member of the rotating internal panel every 3 months to evaluate the safety and efficacy of the trial, the execution of the DSM plan, and compliance with reporting.

Content of DSM Report:

A DSM report will be included in the annual progress report to NIDA and will include:

MAP-Pain Standard Operating Procedures

- Brief description of the trial
- Retention and disposition of study participants (including review of the study's progress toward recruitment goals, treatment adherence, participant attrition/retention rates)
- Q.A. Issues (including analysis of appropriate completion of forms)
- Regulatory Issues (including IRB regulatory actions and changes or amendments to the research protocol approved by the IRB)
- AEs
- SAEs

Case Report Form Completion

Missing data that is available through patient records such as EPIC will be recorded with a notation of such. Data discrepancies will be compared to any source data such as EPIC and corrections made by crossing out the original value, providing the correct value, dating, initialing, and providing a reason for the correction. If there is no hard copy, a comment should be made on REDCap. Missing data or data discrepancies that cannot be resolved by verifying source data will be left as missing.

Consent Form Completion

Consent forms will be evaluated for completeness of all signatures, required initials, and dates. Any missing signatures will be obtained by mailing the patient a copy of the consent form and requesting the signature with the current date. Any missing PI or staff signatures will be obtained and dated with the current date. Patients with missing signatures who are unable, or unwilling, to provide missing signature will be withdrawn from the study and data will not be used.

Electronic Data Verification

Electronic data is entered via the Stanford REDCap system or Perioperative CHOIR. Participants enter responses directly into the electronic system, unless they specifically request responding via phone calls. Hard-copy Case Report Forms are entered into REDCap manually by study staff, after they have completed instructional training and a mock-entry packet that is reviewed by the Research Manager, coordinator, or study monitor.

An additional 10% of data will be randomly verified by study staff prior to data analysis. Verification will occur via visual inspection. Discrepancies will be noted, original source data checked, and the correct value entered. All verified data will be noted with the reviewer's initials and date. Corrections will be noted with the date, initials, and reason for correction. Consistent errors will prompt a more comprehensive review of the data at the PI's discretion.

MAP-Pain Standard Operating Procedures

Primary Efficacy Outcome-Observation Arm

Time to opioid cessation, defined as the first of 2 consecutive reports of opioid cessation on the modified BPI.

Secondary Efficacy Outcomes-Observation Arm

1. Opioid misuse (This will be defined as a score of 9 or higher on the Current Opioid Misuse Measure).
2. Time to pain cessation (This will be defined as the first of five consecutive days of 0 average pain).
3. Time to recovery (First report of patient indicated "Yes" to having recovered from surgery).

Primary Efficacy Outcome-Intervention Arm

Time to opioid cessation, defined as 1st of 2 consecutive reports of return to baseline opioid dose or lower.

Secondary Efficacy Outcomes-Intervention Arm

1. Opioid misuse (This will be defined as a score of 9 or higher on the Current Opioid Misuse Measure).
2. Time to complete opioid cessation, defined as the first of 2 consecutive reports of opioid cessation on the modified BPI.
3. Time to pain cessation (This will be defined as the first of five consecutive days of 0 average pain).
4. Time to recovery (First report of patient indicated "Yes" to having recovered from surgery).
5. Treatment engagement is defined as participation in >50% of phone sessions.
6. Treatment initiation is defined as participation in at least 1 phone session.

Methods for handling missing data and non-adherence to protocol:

Subjects dropping out will be censored at the last known data point. Competing events such as a second surgery will be reasons for censoring at the time of the competing event. Missing data will not be imputed.

Modifications History

Last Updated 10/15/2020 by [name], CRC.

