To attain a more comprehensive understanding of the patient's medication, the research coordinator may need to access the electronic health record (EPIC). EPIC can be used to confirm a patient's medications during the phone screen.

Observation Arm

For the observation arm, patients undergoing any eligible elective surgery at Stanford will be considered for inclusion (See *MAP-Pain Observation Eligible Procedures*).

MAP-Pain Standard Operating Procedures

Patients will be recruited via methods described above. After completion of the phone or email eligibility screening, the research coordinator will contact all participants to obtain full electronic consent for continued study participation.

Intervention Arm

For the intervention arm, the following operations will be considered for inclusion. These are chosen for the appropriateness of the intervention in the context of the surgery, and the willingness of the surgeon to refer eligible patients.

Total Knee Replacement

Total Hip Replacement

Patients will be recruited via methods described above. Initial screening will take place via a brief online eligibility survey, or with an approved phone screen either on the phone or via an in-person interview during the patient's pre-operative appointment. Patients will first be given a description of the study as per the approved phone screen to assess interest and answer any questions (see *Screening Questions* document). Eligibility will be determined by the research coordinator and/or PI, who will input responses to screening questions into REDCap or complete an eligibility checklist at the time of screening (see *Eligibility Checklist* document). Eligibility to continue into the intervention randomization will be confirmed at 2-weeks post-surgery. Patients who do not meet the criteria at this time-point will continue in the observational arm.

Patient Eligibility and Enrollment

Eligible and interested patients:

Priority consent is the Intervention; observational consent is offered secondarily when a patient is ineligible or not interested in the Intervention.

Written Informed consent may be obtained electronically, through completing of the "Electronic Consent" instrument through REDCap.

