Patients who are ineligible or not interested in proceeding with the intervention will be offered enrollment in an observational only arm in which no intervention is given, but participants complete the same baseline preoperative questions, and are followed longitudinally with the same questionnaires. Informed consent for the observational only arm will proceed in the same manner as the full trial using the appropriate, approved consent form (see *Observational Trial Consent with COC* document). Consent is obtained via one of the same three methods mentioned for intervention trial consent.

Patients who are not interested in the clinical trial component or the observational component or unable to participate in either arm due to eligibility concerns will be asked to provide basic de-identified demographic information to allow comparison with participating patients using the Anonymous Data Form (see *Consent for Anonymous Data* document). This may be obtained through discussion with the patient him/herself or by accessing the patient’s medical record. Patients should be asked the reason they chose not to participate.

Patient Rewards

Patients enrolling in either the trial or observational arms of the study are rewarded at three time-points:

- \$20 Amazon EGift Card for completing the baseline questions
- \$20 Amazon EGift Card for completing the 6-month follow-up assessment
- \$20 Amazon EGift Card for completing the 12-month follow-up assessment

MAP-Pain Standard Operating Procedures

Rewards will be distributed automatically from a group of available gift cards stored in the “MAP-Pain Rewards” REDCap Project upon completion of relevant assessments. Alternatively, rewards will be distributed individually by the study staff upon completion of relevant assessments.

EGift Cards will be obtained through the Administrative Assistant ([name]) as needed. The study team will complete and sign a *Human Subjects Incentive Compensation Form (HSIC)* for all participants receiving rewards upon exhaustion of available gift card codes.

Participant Copy of Consent Form & Patient Welcome Packet

Upon completing consent, all participants will be sent a standard welcome email with study team contact information, a copy of their signed consent form, and the Bay Area Resources brochure.

Participant Initiation

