During the pre-surgery call, the coordinator will schedule the post-surgical call fourteen days after the participant’s date of surgery. Unless a specific timeslot is requested by the participant, Post-Surgery calls should be scheduled in the REDCap Calendar at 23:45 for observation participants, and 23:59 for intervention Participants.

Post-Surgical Call

Fourteen days after the participant’s date of surgery, the study coordinator will call the participant to confirm their date of surgery, the date and time they were discharged from the hospital, and verify if the participant has been prescribed and is still using opioid medications for surgical pain. The coordinator will call the patient five times, or until the patient picks up. If possible and necessary, the coordinator should leave a voicemail and specify the name of the patient, the purpose of the call, and leave a return name and number. If appropriate, the coordinator will randomize the study participant immediately after their call.

Randomization

During the Post-Surgical Call (Fourteen days after surgery) the research coordinator should verify whether or not the intervention participant in question has been prescribed and is still using opioid medications for surgical pain. Those who meet this criteria will be randomized to either the Motivational Interviewing and Guided Opioid Weaning intervention, or Enhanced Usual Care. Those who do not meet this criteria will be placed in the Observational arm of the study.

Participants are randomized in the Transfer to Longitudinal Instrument in the MAP-Pain Enrollment REDCap. Upon clicking the “Randomize” button, the coordinator will be prompted to select the surgery type (THR/TKR) and confirm the randomization. The participant will be randomized to “1” or “0”, denoting MI+GOW and EUC respectively. Once randomized, the participant cannot be moved to a different study group, so care must be taken to ensure participant is randomized correctly.

MAP-Pain Standard Operating Procedures

After random group assignment, the Transfer to Longitudinal instrument must be saved to transfer the participant's group assignment to the MAP-Pain: Longitudinal Observation REDCap project. The coordinator will send an email to the appropriate NP, to inform them of a newly randomized participant, and set up an appointment for MI+GOW or EUC sessions to begin.

Blinding and Randomization Methodology

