The first session will be scheduled by the research coordinator; subsequent appointments will be made directly between the NP's and the patient. The first session must be scheduled between 14 and 21 days after the participant's date of surgery. After the initial call, NP's will be responsible for tracking and competing intervention calls.

Intervention Protocol

Participants randomized to MI+GOW will receive the intervention from a single provider ([name]). Of note, participants will have all opioids and additional pain medications prescribed by their surgeon during the study. [name] will only be providing advice regarding participants' opioid medications. Content of the MI call is detailed in the Intervention section above. Treatment engagement is defined as participation in >50% of phone sessions. Treatment initiation is defined as participation in at least 1 phone session.

Longitudinal Follow-up

Scheduling Follow-Up Assessments

Electronic surveys will be sent out automatically based on confirmed dates of surgery. Distribution of online assessments will occur via the REDCap survey invitations calendar defined in the Longitudinal Observation Project, beginning seven days after the date of surgery. A patient's official date of surgery will be entered into the "Pre-Surgery Call" instrument in REDCap during the Pre-Surgery call, and confirmed during the Post-Surgery call. The study team member may verify the date of surgery and time of discharge in EPIC and record it on the "Post-Surgery Call" instrument.

Medical Chart Review

Research team member will review the patient's medical record for information required on the case report form.

Compliance Monitoring

Participant compliance with follow-up assessments will be assessed weekly through an automated reporting dashboard. Patients failing to complete two consecutive follow-up assessments be contacted

MAP-Pain Standard Operating Procedures

by the research coordinator, to encourage continued participation. The coordinator may offer to limit the participant's follow-up to monthly surveys, to maintain follow-up data collection for the participant.

Survey Frequency Reduction

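### Hip and knee patients who consented to the intervention are sorted into the observational arm by day-14 opioid use, so pooling them biases that arm's time to opioid cessation towards early cessation

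*Protocol*

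**What the plan says.** The sorting rule appears twice in the protocol. Under Randomization, the coordinator checks on day 14 whether an intervention participant "has been prescribed and is still using opioid medications for surgical pain". If so: "Those who meet this criteria will be randomized to either the Motivational Interviewing and Guided Opioid Weaning intervention, or Enhanced Usual Care". If not: "Those who do not meet this criteria will be placed in the Observational arm of the study". The Intervention Arm text under Screening gives the same rule: "Patients who do not meet the criteria at this time-point will continue in the observational arm".

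The observational arm has its own enrolment goal of 558 (Study Overview) and its own primary outcome (Primary Efficacy Outcome-Observation Arm): "Time to opioid cessation, defined as the first of 2 consecutive reports of opioid cessation on the modified BPI". Outcome surveys are sent weekly, "beginning seven days after the date of surgery" (Scheduling Follow-Up Assessments), so the outcome is already being recorded when the sorting takes place.

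The arm has two other main entry routes, neither tied to day-14 use. Under Observation Arm, "patients undergoing any eligible elective surgery at Stanford will be considered for inclusion". Under Patients not interested or ineligible, the protocol adds the second route: "Patients who are ineligible or not interested in proceeding with the intervention will be offered enrollment in an observational only arm".

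The SAP's Analytic Plan describes the comparison of randomised groups only. Neither document says how patients routed at day 14 enter an analysis of the observational arm.

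**The concern.** A patient in the routed stream belongs to the observational arm largely because opioid use had ended, or never began, within two weeks. A patient from the same source who was still using at two weeks has left for the randomised groups. The early part of the cessation curve is kept and the later part removed.

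If these patients are pooled with the others, the share stopped by day 14 is too high and the median time to cessation too short. The distortion is greatest for hip and knee replacement, the only operations to which the rule applies. Comparisons between surgery types within the arm would inherit it, since joint replacement would look quicker to recover from than it is. The stream need not be small: the protocol gives intervention consent priority and offers observational consent second.

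**Working it through.** **Plan's own figures.** The plan states no figure for this point. The two enrolment goals are consistent with inflation by N/(1 − d): 474/0.85 = 557.6, rounded up to 558, and 198/0.90 = 220. The bases 474 and 198 are back-solved, not stated. No day-14 rate and no consent share is given, so the size can only be illustrated.

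**Check 1: whole arm, share stopped by day 14.** Assumptions: the 220 are randomised patients; routed patients count towards the 558; all observational patients share one day-14 rate; failing the criterion is treated as cessation. Let s be the share still using at day 14.

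- Routed patients: R = (220/s) × (1 − s)
- Apparent share stopped: [R + (558 − R)(1 − s)]/558

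| s | R | R/558 | Apparent share stopped | True share |
|---|---|---|---|---|
| 0.80 | 55 | 10% | (55 + 503 × 0.20)/558 = 28% | 20% |
| 0.70 | 94 | 17% | (94 + 464 × 0.30)/558 = 42% | 30% |
| 0.60 | 147 | 26% | (147 + 411 × 0.40)/558 = 56% | 40% |
| 0.50 | 220 | 39% | (220 + 338 × 0.50)/558 = 70% | 50% |

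If the 220 instead counts everyone who consents to the intervention, R = 220(1 − s). At s = 0.80 that is 44 patients, and (44 + 514 × 0.20)/558 = 26%. At s = 0.50 it is 110 patients, and (110 + 448 × 0.50)/558 = 60%. The bias is smaller but in the same direction.

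**Check 2: hip and knee patients within the arm.** Let q be the true share stopped by day 14 and c the share who consented to the intervention. The arm keeps all of the 1 − c and only the stopped part of c, so the apparent share is q/[(1 − c) + cq]. For q = 0.30:

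- c = 0.25: 0.30/0.825 = 0.36
- c = 0.50: 0.30/0.65 = 0.46
- c = 0.75: 0.30/0.475 = 0.63
- c = 1: 0.30/0.30 = 1.00

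**Check 3: median time to cessation.** Assume exponential times with a true median of 28 days, so λ = ln 2/28 and the share stopped by day 14 is 1 − exp(−14λ) = 0.293. Let w be the routed share of the arm, with routed patients restricted to times up to 14 days. The survival curve is (1 − w)exp(−λt) + w[1 − (1 − exp(−λt))/0.293] up to day 14, and (1 − w)exp(−λt) after it. Setting it to 0.5:

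- w = 0.10: apparent median 23.7 days
- w = 0.25: 16.4 days
- w = 0.50: 10.4 days

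With a true median of 56 days, the apparent medians are 47.5, 32.8 and 11.9 days. All three checks point the same way, and the size is set by shares that the documents do not give.

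**The case against.** Several points on the other side stand, and they set the limits of the concern.

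- A reader might infer that the whole arm is selected on its outcome. It is not. Patients having other elective surgery, decliners, and patients ineligible for the intervention enter whatever their day-14 use, so continuing hip and knee users are not all removed.
- A reader might infer that routed patients enter because the endpoint has already occurred. The criterion and the endpoint differ. The criterion asks about prescribed opioids used for surgical pain; the endpoint is the first of two consecutive reports of no opioid use at all. A patient never prescribed opioids fails the criterion without having stopped anything. A patient using opioids only for other pain fails it without reaching the endpoint.
- A reader might infer that the trial's main result is biased. The rule is applied before randomisation and equally to both groups, so the MI+GOW versus EUC comparison is untouched.
- The documents do not say that randomised patients are left out of an observational analysis. Intervention participants are also moved to the longitudinal project after surgery, and surveys start at day 7, so early data should exist for both streams. This makes the problem repairable. It does not remove it, because no rule says those data will be used, and the arm as described excludes them.
- The protocol's table of contents lists a data analysis plan and a power section that do not appear in the text supplied. An observational analysis rule may exist there, so the conclusion is limited to the text in hand.

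Dropping all routed patients would be a poor main remedy. It leaves only those hip and knee patients who declined or were ineligible, which is another selected group, and on the assumptions of check 1 it discards 10% to 39% of the arm.

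**Conclusion.** The concern holds for one entry stream. For hip and knee patients who consented to the intervention, early status on the outcome decides whether they are in the observational arm. Used as written, with that stream pooled as if unselected, the arm's primary outcome is biased towards early cessation, mainly for joint replacement. Nothing in the supplied text corrects this.

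The direction is secure; the size is not. Under the assumptions of check 1, day-14 cessation is overstated by 8 percentage points (28% against 20%) to 20 points (70% against 50%). Smaller routed shares, or routed patients not counted in the 558, would reduce this. The change should be made before the observational data are analysed. It has no bearing on the validity of the randomised comparison.

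**What to change.** 1. Flag every patient routed at day 14. Consent type and randomisation status are already in REDCap, and a routed patient is one with intervention consent who was not randomised. Report how many of the 558 are routed. State how patients not reached after the five day-14 calls are classified, and identify randomised patients later moved to observation-only follow-up under Schedule.
2. Define the observational cessation analysis by the pre-surgical cohort, stratified by surgery type. Keep later-randomised patients in the risk set from surgery and censor them at randomisation. This restores the continuing users to the day-14 denominator. After day 14 the hip and knee estimate rests mainly on decliners and ineligible patients, and the report should say so. Because reports are weekly, also state how cessation is dated when a routed patient's first zero report comes after the day-14 call; otherwise some of the selection remains.
3. Add two sensitivity analyses. (a) Restrict to patients who consented directly to the observational arm, noting who the hip and knee patients there are. (b) For hip and knee, combine routed patients with EUC patients weighted by the inverse of the allocation probability. The allocation ratio is not stated in the text and must be supplied. EUC patients receive calls, so this is not an untreated course.

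The cost is a derived flag, a short paragraph in the analysis plan, a little more analysis work, and a smaller effective sample after day 14. Recruitment, randomisation and patient care do not change.
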